Official Title: Aspirin as Adjuvant Therapy in Young Psychotic Patients NCT number: NCT02685748

Study Protocol and Statistical Analysis Plan

Effect of adjuvant aspirin therapy on neurological soft signs and PANSS in young psychotic patients

A randomized, interventional, double-blind, placebo-controlled clinical trial

Protocol name:	Aspirin2016.2
Date:	25 October 2016.
Donor:	Stanley Medical Research Institute, [name], [name] 20815, SAD
Sponsor:	Clinic for Mental Diseases "[name]", [name], Serbia
Principal Investigator, Grant Holder:	MD [name], psychiatrist
Co-investigators:	MD/PhD [name], neuropsychiatrist MD [name], psychiatrist MD [name], psychiatrist

Background:

The clinical trial team would conduct a randomized, interventional, double-blind, placebo-controlled study in two parallel groups of patients who were neuroleptically naive or previously minimally medicated (who did not take antipsychotics during the previous 6 months) with the illness duration of up to seven years. Patients of both sexes, ages 18 to 28, would participate in the trial, in accordance with the tenth revision of the International Classification of Diseases (ICD10), they would meet the diagnostic criteria for the illnesses ranging from F 20 to F 29. After meeting the inclusion and exclusion criteria and having signed an informed consent form, the patients would be randomized into two groups:

Experimental group - EG: antipsychotic + Aspirin

and

Control group – CG: antipsychotic + placebo.

The EG patients would be administered 1000 mg aspirin pro die with gastric protection pantoprazole 40 mg pro die, both medicines in two doses during 6 weeks of hospital treatment at Clinic form Mental Disorders "[name]". The trial would last for 18 months and would include the total of 100 to 120 patients.

Objective and hypotheses:

The objective of the trial would be to determine the effect of adjuvant aspirin therapy on neurological soft signs, positive and negative syndrome in schizophrenia, cognition, inflammatory factors and cytokine profile.

Working hypotheses:

- 1. Changes in PANSS and MoCA scores as well as inflammation factors in both patient groups, more in the experimental group.
- 2. Changes in the cytokine profile in both patient groups.

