- 3. In case of significant change of SNS and cytokine profile in the experimental group the results would support the cytokine hypothesis. If there were no significant changes in the SNS in the experimental group, the results would support the SNS as a trait of schizophrenia.

Clinical Trial Design:

A randomized, interventional, double-blind, placebo-controlled clinical trial in two parallel groups of patients who were neuroleptically naive or previously minimally medicated (who did not take antipsychotics during the previous 6 months) with the illness duration of up to seven years. Patients of both sexes, ages 18 to 28, would participate in the trial, in accordance with the tenth revision of the International Classification of Diseases, would meet the diagnostic criteria for the illnesses ranging from F20 to F29. Upon fulfilment of inclusion and exclusion criteria and signed Informed consent form, they would be randomized in two groups: experimental (EG) and control group (CG). Patients belonging to the control group would be administered antipsychotic therapy and placebo, whereas patients in the experimental group would be administered regular antipsychotic therapy and aspirin. EG patients would be administered 1000 mg aspirin pro die with gastric protection- pantoprazole 40 mg pro die, both medicines in two doses in duration of 6 weeks.

A software application specialized in the randomization of subjects for clinical trials -*Sealed Envelope* - will be used for randomization. The obtained list will be in possession of one co-investigator and only he or she will know which group the patient belongs to. Only upon completion of the trial, after taking the serum samples from the last patient, and cytokine profile analysis (cytokine profile analysis would be performed at the end of the trial, after the serum sample from the last patient was taken at both test times) would the patient's belonging to the EG or CG group be revealed.

The co-investigator in charge of randomization would give out the medicine boxes and the medicines would all look identical - packed in the same capsules for overcapsulation by the company **Capsugel**. Placebo tablets would be manufactured by Galenika A.D. The patient would be administered Bayer's Aspirin tbl. á 500 mg and Nolpaza tbl. á 20 mg produced by Krka-Farma D.O.O.

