Three visits are planned. The first visit after admission to the Clinic. If the patient fulfils the inclusion criteria and none of the exclusion criteria (anamnestic data, somatic and psychiatric examination), and after the Informed consent form has been signed, PANSS scale test and blood sample would be taken for laboratory analysis. Laboratory analysis would be complete blood count (RBC, WBC, PTC, Hgb, Hct), sedimentation, C reactive protein, blood biochemical analysis (glycaemia, cholesterol, triglycerides, transaminases, CK, bilirubin, uric acid, creatinine, urea), and electrolytes (Na, K). Th1, Th2 and Th17 cytokines would be subject to the immunological assays. Each patient would be given an identification number (from one upwards) and the tubes with serum for the cytokine profile would be labelled with the same number, in terms of x/y, where x is the patient's identification number and y- may be "1" or "2" ("a" or "b"), where "1" or "a" would mean the first blood draw (at the beginning of the trial) and the number "2" or "b" - the second blood draw (at the very end of the trial).

After calming down of the acute signs of psychosis, between the third and fifth day of hospitalization, the second visit would be made when testing of the neurological soft signs would be performed according the Heidelberg Soft Neurological Signs Scale, the MoCA Cognitive Assessment Scale, and then the patient would be randomized to an experimental or control group if he/she meets the inclusion and no-exclusion criteria, if there are no somatic contraindications (with a stable ECG), and if he/she still wishes to participate in the trial.

The staff of the ward where the patient would be accommodated would be given two boxes of medicines labelled "Clinical Trial Medication 1" and "Clinical Trial Medication 2" that would be administered to patients – one medicine from each box, in the morning and in the evening.

After 6 weeks from the second visit (+/- 3 days), the third visit would be made when the patient would be examined, the PANSS, MoCA and Heidelberg scales testing repeated, and the blood sample taken again for laboratory analyses - inflammatory factors and cytokine profiles.

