Continuous variables will be displayed descriptively using the minimum and maximum values, mean values and standard deviation. Categorical variables will be presented descriptively using absolute and relative frequency as well as graphically using a pie chart.

Kolmogorov-Smirnov or Shapiro-Wilk test, depending on sample size, will be used to check the normality of data distribution, as well as graphical method of using histogram. If the data follow the normal distribution, parametric tests will be used for the statistical analysis of the data; otherwise the corresponding non-parametric tests will be used.

For the analysis of significant continuous variables over time, the Paired Samples t Test will be used if the data follow a normal distribution or the Wilcoxon test if the data do not follow the normal distribution. Significant results will be presented graphically using a bar chart or boxplot.

For the analysis of significant difference of continuous variables between the control and experimental groups, the Independent Samples t Test will be used if the data follow a normal distribution or the Mann-Whitney test if the data do not follow the normal distribution. Significant results will be presented graphically using a bar chart or boxplot.

For the analysis of the dependence between two continuous variables, the value of Pearson's or Spirman's correlation coefficient will be interpreted. In the case of strong correlations, the dependence will be shown both by the regression equation and graphically using the scatterplot.

For the analysis of the dependence between the two categorical variables, a Chi-squared test, that is, a Fisher's exact-dependency test will be used. The results will be presented graphically using a bar cluster graph.

The results will be considered statistically significant if the p value is less than 0.05.

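### No primary outcome and one p<0.05 rule for everything: if aspirin is inert, the chance of a false between-arm positive is 18–23% over the five objective domains and 9–10% over the two title outcomes (assumed correlation 0.5 to 0)

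*Combined protocol and SAP*

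**What the plan says.** The section "Statistical analysis plan" closes with one decision rule: "The results will be considered statistically significant if the p value is less than 0.05". For the comparison of arms it gives one generic instruction, "For the analysis of significant difference of continuous variables between the control and experimental groups, the Independent Samples t Test will be used", with Mann-Whitney as the substitute when normality fails. The variables are neither listed nor ranked.

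The section on objective and hypotheses says the trial is to determine the "effect of adjuvant aspirin therapy on neurological soft signs, positive and negative syndrome in schizophrenia, cognition, inflammatory factors and cytokine profile". That makes five domains, side by side. The study title is narrower: "Effect of adjuvant aspirin therapy on neurological soft signs and PANSS in young psychotic patients".

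The working hypotheses do not follow the title:

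- Hypothesis 1: "Changes in PANSS and MoCA scores as well as inflammation factors in both patient groups, more in the experimental group". Soft signs are absent.
- Hypothesis 2: "Changes in the cytokine profile in both patient groups". No difference between arms is predicted.
- Hypothesis 3: "In case of significant change of SNS and cytokine profile in the experimental group the results would support the cytokine hypothesis". This needs two findings together, and it concerns a theory of the disease.

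The laboratory domains hold more than one variable each. Under Clinical Trial Design, sedimentation and C-reactive protein are both measured, and "Th1, Th2 and Th17 cytokines would be subject to the immunological assays". No primary outcome, hierarchy, multiplicity adjustment or power calculation appears anywhere.

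**The concern.** A 5% threshold limits the false-positive rate of one test. It does not limit the rate for a claim that may rest on any of several tests. Here a lone positive result on MoCA, CRP or a single cytokine could be reported as an aspirin effect without departing from the plan, and the headline outcome could be chosen after unblinding. A reader of a positive report could not tell whether the highlighted outcome was the intended one or the one that happened to cross 0.05.

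**Working it through.** The plan gives no family-wise error rate, power or sample-size derivation, so there is no figure of its own to reproduce. Its only input is the per-test threshold.

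**Inputs from the document**

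- Threshold: 0.05 for every result (statistical analysis plan).
- Outcomes: five domains in the objective, two in the title.
- Total sample: 100 to 120 (Background).

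**Assumptions**

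- Two-sided tests, since sidedness is not stated.
- 1:1 allocation and no dropout, giving 50 to 60 per arm.
- A common pairwise correlation ρ between outcomes, taken as 0 to 0.5, with 0.7 shown as well. The document gives none.
- For the four-test and eight-test counts, CRP and sedimentation stand for the inflammatory factors. The eight-test count also takes one cytokine per Th class.

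**Family-wise error if aspirin is inert**

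For k independent tests, P(at least one p<0.05) = 1 − 0.95^k:

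- k=2: 1 − 0.9025 = 0.0975
- k=5: 1 − 0.7738 = 0.2262

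For equicorrelated normal statistics with c = 1.96, in either direction:

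P = 1 − ∫ φ(u) [Φ((c − √ρ·u)/√(1−ρ)) − Φ((−c − √ρ·u)/√(1−ρ))]^k du

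For differences favouring aspirin only, the bracket is Φ((c − √ρ·u)/√(1−ρ)). At ρ=0 this reduces to 1 − 0.975^k.

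| Tests counted | k | Either direction: ρ=0 | ρ=0.3 | ρ=0.5 | ρ=0.7 | Favouring aspirin: ρ=0 | ρ=0.5 | ρ=0.7 |
|---|---|---|---|---|---|---|---|---|
| Title: PANSS, soft signs | 2 | 0.0975 | 0.0951 | 0.0907 | 0.0835 | 0.0494 | 0.0454 | 0.0417 |
| Hypothesis 1: PANSS, MoCA, CRP, sedimentation | 4 | 0.1855 | 0.1740 | 0.1558 | 0.1304 | 0.0963 | 0.0779 | 0.0652 |
| One test per objective domain | 5 | 0.2262 | 0.2089 | 0.1828 | 0.1484 | 0.1189 | 0.0915 | 0.0742 |
| Three scales, CRP, sedimentation, one cytokine per Th class | 8 | 0.3366 | 0.2997 | 0.2501 | 0.1909 | 0.1833 | 0.1252 | 0.0954 |

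The reference for a single test is 0.05 in either direction and 0.025 favouring aspirin. Simulated two-sample t tests with 50 and 60 per arm (60,000 replicates each) agree at ρ=0 and ρ=0.5: 22.7–22.8% and 18.4–18.5% for five tests, about 9.8% and 9.0% for two.

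**Error under the proposed change**

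Holm on two primaries, both null, makes a false rejection only if the smaller p is below 0.025. At ρ=0 that is 1 − 0.975² = 0.0494. At ρ=0.3, 0.5 and 0.7 it is 0.0484, 0.0465 and 0.0430.

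**Power under the proposed change**

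- Difference detectable with 80% power (two-sample t), at 0.05 and then 0.025: 0.566 and 0.625 SD at 50 per arm; 0.516 and 0.569 SD at 60 per arm.
- Power at 0.566 SD, 50 per arm, threshold 0.025: 0.709.
- If both outcomes truly differ by 0.566 SD (40,000 simulated trials, 50 per arm, ρ=0, 0.3, 0.5): at least one detected in 0.915, 0.883 and 0.852; each outcome detected in 0.758–0.776.
- Baseline adjustment multiplies the detectable difference by √(1 − r²), where r is the correlation between baseline and third visit. At an assumed r=0.5 and 50 per arm: 0.566 × 0.866 = 0.490 SD at 0.05, and 0.625 × 0.866 = 0.541 SD at 0.025.
- Adjusted testing at 0.025 matches unadjusted testing at 0.05 when r = √(1 − (0.566/0.625)²) = 0.42.

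**The case against.** The absence itself is not in dispute. The objections concern its size and the remedy.

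**Direction.** The headline percentages include results showing aspirin to be worse. For a claim of benefit the right figures are 9–12% over five domains and about 5% over two, against 2.5% for one test. That is correct, and both sets are given here. The proportional inflation is similar either way. A favourable direction also has to be assumed for each variable, and the document defines none for cytokines.

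**Correlation.** The range of 0 to 0.5 is assumed. At 0.7 the either-direction figures fall to 15% (five tests) and 8% (two). Both remain above 5%.

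**Five routes to a claim.** The title points to two outcomes, hypothesis 2 predicts no between-arm difference, and hypothesis 3 is a conjunction, which does not inflate error in this way. Nobody has written that one positive cytokine would count as efficacy. This is fair as far as it goes, but nothing excludes it, and the most lenient reading (title outcomes only) still gives 9–10%. Each individual test does keep its nominal 5%; what is uncontrolled is the family-wise rate.

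**The remedy and hypothesis 3.** The plan would read no significant change in soft signs as evidence that they are a trait, so a stricter threshold could make that conclusion easier to reach wrongly. With 50 per arm, a true soft-signs difference of 0.566 SD and no PANSS difference, the chance of missing it rises from about 20% to about 29%. This applies only if hypothesis 3 is judged between arms, whereas its text speaks of change within the experimental group. A single primary at 0.05 avoids the stricter threshold.

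**Loose ends.** The remedy needs one score per scale, and the co-investigator who holds the allocation list should not take part in the choice. Both points are accepted.

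**Conclusion.** The concern holds. Followed as written, the plan gives a family-wise false-positive rate well above the 5% it appears to promise. For differences in either direction and an assumed correlation of 0.5 to 0, the ranges are 9–10% for the two title outcomes, 16–19% for hypothesis 1 read as four tests, 18–23% for one test per domain and 25–34% for eight tests. Favouring aspirin only, they are about 5%, 8–10%, 9–12% and 13–18%.

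These figures rest on the assumed correlations, two-sided testing and the stated test counts. The laboratory domains contain several variables, so one test per domain is a low count. Within-arm paired tests and correlation analyses fall under the same 0.05 rule and are not included.

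This should be corrected: it bears on any positive claim, and wording is enough to resolve it.

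**What to change.** Record the following in the statistical analysis plan before the allocation list is opened, with the co-investigator who holds that list taking no part in the choice.

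1. Name PANSS and the Heidelberg soft-signs scale at the third visit, experimental against control group, as the two primary outcomes, with one stated score per scale. Test them by Holm at an overall two-sided 0.05. A single primary outcome at 0.05 is an acceptable alternative.
2. Label MoCA, inflammatory factors and cytokines secondary or exploratory.
3. Restrict claims that aspirin is effective to the primary between-arm tests.

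**Effect.** With two primaries under Holm, the family-wise error if aspirin is inert is 4.7–4.9% (correlation 0.5 to 0).

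**Cost.** No new patients, visits or data are needed. With two primaries, the difference detectable at the first Holm step rises from 0.57 to 0.62 SD at 50 per arm and from 0.52 to 0.57 SD at 60 per arm. At 0.57 SD and 50 per arm, power at that step falls from 80% to 71%. If both outcomes truly differ by that amount, power is 76–78% per outcome and 85–92% for at least one.

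Baseline adjustment would offset the loss relative to the planned unadjusted test once the baseline to third-visit correlation exceeds about 0.42. Compared like for like, the loss from the stricter threshold remains. A single primary outcome carries no such cost.
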